#### 8.2.8 Administration

See Section 5.3.2. During combination treatment, mirvetuximab soravtansine should be administered first, followed by pembrolizumab. Details of the dose level and total dose administered should be documented in the source records

Pembrolizumab administration will be monitored to ensure compliance and proper documentation of the infusion procedure as well as management of infusion reactions should they occur.

#### 8.2.9 Ordering

Investigative sites will order their own supply of pembrolizumab.

#### 8.2.10 Accountability

The investigator, or a responsible party designated by the investigator, should maintain a careful record of the inventory and disposition of the agent using the NCI Drug Accountability Record Form (DARF) or another comparable drug accountability form. (See the NCI Investigator's Handbook for Procedures for Drug Accountability and Storage.)

8.2.11 Destruction and Return

Expired investigational product will be destroyed at the site per institutional policy. Upon completion or termination of the study, all unused and/or partially used investigational product will be destroyed at the site per institutional policy.

#### **BIOMARKER, CORRELATIVE, AND SPECIAL STUDIES**

#### 9.1 **Biomarker Studies**

#### 9.1.1 FRa Expression - Integral Biomarker

All patients must submit archived or new biopsy tumor tissue, or formalin-fixed, paraffin embedded (FFPE) block of sufficient size to allow for sectioning of ten 5-micron tissue sections or five unstained slides for central analysis of FR $\alpha$  expression prior to enrollment.

The tumor samples will be analyzed centrally for FRα expression by Immunohistochemistry (IHC) in the Companion Diagnostics Pharma Services CAP-accredited and CLIA-certified laboratory and Pathology Services at Ventana Medical Systems, Inc.

Only patients with confirmation of FR $\alpha$  positivity by the Ventana FOLR2.1 IHC assay (Ventana Medical Systems. Tucson, AZ) will be eligible to enroll in the study.

Samples will be shipped Monday – Thursday to (address below): CDx CAP/CLIA Laboratory Ventana Medical Systems, Inc. Attn: CDx CAP/CLIA Laboratory [name]

9.1.2 Microsatellite Stability – Integral Biomarker

Prior to enrollment, patients must have documented MSS by routine methods including MMR IHC, MSI PCR or MSI by Next Generation Sequencing (NGS). Only patients with intact expression of all four MMR proteins by IHC, or MSS by PCR or NGS from a CLIA-certified laboratory will be eligible to enroll.

#### 9.2 Laboratory Correlative Studies (FFPE Tumor Tissue)

Correlative studies may be performed in the Immune Oncology and DNA Repair Centers here at DFCI or Ventana Medical Systems. Depending on funding availability these studies may include: i) determination of CD3+, CD8+ TILs, CD8+/CD4+FOXP3+ TIL ratio, CD137+CD8+ TILs, CD137+CD8+/CD4+FOXP3+ TIL ratio, peritumoral lymphocytes and correlation with response; ii) expression of immune checkpoints including TIM-3, LAG-3, CTLA-4, PD-L2, PD-L1, PD-1, IDO and correlation with response; iii) targeted next generation sequencing (OncoPanel) to determine specific genetic alterations and correlate with response. Where OncoPanel sequencing has already been performed on patient samples clinically or through DF/HCC protocols 11-104, 17-000, and 20-000, we may plan to access these results. Additionally, we will characterize the FOLR1 expression in uterine serous cancers and overlap with other potential targets of interest, which may include but is not limited to HER2 and Trop2.

If archival tumor tissue in the form of unstained slides are used for central analysis of FR $\alpha$  expression prior to enrollment, the remaining five unstained slides should be shipped to the DFCI coordinating center along with the manifest form provided to each site. Please send the samples to:

[name] Dana-Farber Cancer Institute [name] Email contact: [name]\[contact]; [name]\[contact]

#### STUDY CALENDAR

Baseline screening evaluations are to be conducted within 14 days prior to start of protocol therapy. Scans and x-rays must be done  $\leq 4$  weeks prior to the start of therapy. In the event that the participant's condition is deteriorating, laboratory evaluations should be repeated within 48 hours prior to initiation of the next cycle of therapy.

Assessments must be performed prior to administration of any study agent. Study assessments and agents should be administered within  $\pm$  3 days of the protocol-specified date, unless otherwise noted.

	Due Stude		Cycle 1		Cycle 2 and beyond	
	Pre-Study	Day 1	Day 8	Day 15	Day 1	Off-treatment visite
Mirvetuximab Soravtansine		X			Х	
Pembrolizumab		X			Х	
Archival FFPE sample	X					
Collection of MSS documentation	x					
Demographics	x					
Medical history	x					
Concurrent medications	х	X				Х
Physical exam	x	X	Х	X	X	Х
Vital signs	x	X	Х	X	X	Х
Height	x					
Weight	X	X	X		Х	Х
Pulse Oximetry	X	X	X	X	X	
ECOG Performance status	X	X	X		X	Х
CBC w/diff, plts	X	X	X	X	X	Х
Serum chemistry a	X	X	X	X	X	Х
TSH	X	X			X	Х
PT/INR/PTT	X					Х
EKG (as indicated)	X					Х
Pulmonary Function Tests c	X					
Ophthalmic examinations d	X	Every oth	er cycle (from t	ime toxicity fi	rst reported, until resolve	ed to baseline or ≤Grade 1)
Schirmer Test d	X	For patients who experience treatment-emergent eye disorders, the Schirmer Test will be repeated at the first on-study ophthalmic examination and at subsequently if clinically indicated				
Ocular Symptom Assessment d	x	X			x	Х
Adverse event evaluation		X				X
Tumor measurements	X	Tumor meas week). I	surements are r Documentation	epeated every ( (radiologic) m	$\frac{2 \text{ cycles } (6 \text{ weeks}, \pm 1)}{\text{ust be provided for}}$	

			participants removed from study for progressive disease.					
B-HCG		Xb						
Lubricatin administra	ng artificial tears			Dail	y as directed f		Xg	
Corticoste administra	Corticosteroid eye drop administration Six times daily on Days 1-4 and four times daily on Days 5-8 of each cycle f		X g					
a.	Albumin, alkali	ne phospha	tase, total bi	lirubin, bicart	onate, BUN,	calcium, chloride, ci	reatinine, glucose, LDH,	
	phosphorus, por	tassium, tot	al protein, S	GOT [AST], S	SGPT [ALT],	sodium.		
b.	Serum pregnan	cy test (wor	nen of childt	bearing potent	nal) should be	e done within 3 days	of the first dose of study	
c.	
 
treatment.
 
Pulmonary function tests (PFTs) should include spirometry, diffusion capacity, and lung volumes. PFTs will be performed at screening and in the event of nulmonary symptoms as clinically indicated
 
							
d.	Baseline ophtha	almic exams	s will be perf	ormed by a b	oard-certified	ophthalmologist and	d will include the	
	following: visua	al acuity, in	direct fundo:	scopy, slit lan	np examinatio	n under dilatation, ir	ntraocular pressure	
	measurement, a	nd corneal	photography	. A Schirmer	test will be pe	erformed at baseline	for all patients, and for	
	patients who ex	perience oc	ular sympton	ns, it will be	repeated at the	e first on-study ophtl	halmic examination and at	
	subsequently if	clinically in	ndicated. Ma	y be performe	ed within 14 d	lays of Cycle 1, Day	1. Ocular symptom	
	assessment will be performed prior to the start of each cycle by the treating physician or other qualified							
	individual. If the subject reports ocular symptoms then IMGN853 will be stopped and the subject will then be							
	referred to an o	phthalmolo	gist for a cor	nplete examir	nation (detaile	d in full protocol). P	atients who experience	
	ocular toxicity	will have a	complete op	nthalmologic	exam perform	ed every other cycle	e, including patients with	
	blurred vision b	out normal e	eye exams. A	Il patients wh	o experience	ocular toxicity will t	be followed until	
	resolution.	valuation (	)ff tractman	wigit will as	ur within 7 d	ave of the design to	discontinuo studu	
С.	treatment Parti	valuation. C	be followed	for 30 days a	fter the last d	ays of the decision a	adverse events	
	Participants wil	l be follow	ed for 3 year	by phone aff	ter removal fr	om study or until de	adverse events.	
	first. Survival s	tatus should	be checked	every 6 mont	hs during that	time	aui, willelievel occurs	
f.	See Appendix I	D. The patie	ent should co	ntinue use of	the corticoste	roid eve drops per th	e ophthalmologist	
	recommendatio	n after disc	ontinuation	fmirvetuvim	ah soravtansi	ne. The natient shoul	d continue the lubricating	

recommendation after discontinuation of mirvetuximab soravtansine. The patient should continue the lubricating eye drops for 4 weeks following discontinuation of mirvetuximab soravtansine.

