#### TREATMENT PLAN

#### 5.1 Treatment Regimen

Treatment will be administered on an outpatient basis.

Following premedications, mirvetuximab soravtansine will be administered at 6 mg/kg by Adjusted Ideal Body Weight (AIBW) intravenously on Day 1 of a 21-day cycle. Then, pembrolizumab will be administered intravenously over 30 minutes at 200 mg flat dose on Day 1 of 21-day cycle (one cycle =21 days), after all procedures and assessments have been completed. Study medications may be administered up to 3 days before or after the scheduled day of administration of each cycle due to administrative reasons.

The duration of treatment with the combination will be until progression or adverse event up to 35 cycles. Beyond 35 cycles, mirvetuximab soravtansine will be continued until progression or adverse event.

Agent	Dose	Route	Schedule	Cycle Length
Mirvetuximab soravtansine	6 mg/kg	IV before	Day 1 each	
(IMGN853)*	(AIBW)	Pembrolizumab	cycle	21 days
		+/- 10 min**		$\frac{21 \text{ uays}}{(2 \text{ weaks})}$
Pembrolizumab	200 mg	IV over 30	Day 1 each	(5 weeks)
		minutes -5/+10	cycle	
		min		
*Note: Mirvetuximab soravtansine is incompatible with 0.9% sodium chloride (saline)				
** Infusion rate will vary based on patient tolerability as described in Section 5.3.1				

Reported adverse events and potential risks are described in Section 7. Appropriate dose modifications are described in Section 6. No investigational or commercial agents or therapies other than those described below may be administered with the intent to treat the participant's malignancy.

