## 5.4.2 Other supportive care

- Antiemetic (e.g. 5-HT3 serotonin receptor antagonists such as palonosetron, granisetron or ondansetron), antidiarrheal (e.g. loperamide) medications, and other supportive care may be used at the discretion of the treating physician, unless prohibited below in Section 5.4.3.
- Patients are strongly advised to avoid using contact lenses while on mirvetuximab soravtansine.

- Baby shampoo and a soft cloth should be used to clean the eyes, and a warm compress at bedtime may be used to decrease any possible inflammation on the eyelid's surface.
- The use of UVA/UVB sunglasses is recommended in full daylight during the course of the study.
- The use of temporary lower punctal plugs to increase lubrication of the eyes is optional if lubricating artificial tears and corticosteroid eye drops are not sufficient.

The management and dose modification for ocular symptoms is outlined in Section 6.

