If a patient develops ocular symptoms of any grade, the patient is required to have a complete examination by an ophthalmologist. If a patient develops  $\geq$  CTCAE Grade 2 ocular symptoms, treatment with mirvetuximab soravtansine will be interrupted. Therapy may resume if ocular symptoms improve to Grade 1 or baseline within 28 days of the next scheduled mirvetuximab soravtansine dose (refer to Table 3 for details). Subsequent eye examinations will be scheduled to occur in every other cycle going forward, from the time that the AE was initially reported, and at either the End of Treatment visit or 30-day follow-up visit following treatment discontinuation, even if the results of the patient's ocular exam shows no obvious clinical findings. Management of treatment-emergent ocular AEs with inflammatory characteristics should include corticosteroid eye drops and/or other measures as indicated by an ophthalmologist.

CTCAE v5.0 Severity Grade*	Management	Guidelines for Mirvetuximab Soravtansine Dose Modifications
Grade 1	
 
Complete eye exam as outlined in Study Calendar and Appendix C.
 
Monitor for worsening symptoms
 
Repeat complete exam as clinically indicated, at least every other cycle (from point at which toxicity first reported) at a minimum
 
	Continue mirvetuximab soravtansine dosing
Grade 2	
 
Complete eye exam as outlined in schedule of clinical assessments (Study Calendar and Appendix C).
 
Repeat complete exam as clinically indicated
 
Patients should have weekly symptomatic ocular assessments until the symptoms resolve to Grade 1 or baseline or are deemed to irreversible by investigator
 
Repeat complete exam as clinically indicated, at least every other cycle (from point at which toxicity first reported) at a minimum
 
	
 
Hold mirvetuximab soravtansine dosing until AE has resolved to Grade 1 or better.
 
Patients with ocular symptoms lasting < 14 days may be allowed to resume mirvetuximab soravtansine at the same dose level
 
Patients with ocular symptoms lasting ≥ 14 days but no more than 28 days may resume mirvetuximab soravtansine reduced by one dose level
 

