# Table 3: Management of Ocular Disorders

	Tototot Version Bute. December 11, 2025				
Grade 3	
 
Complete eye exam as outlined in schedule of assessments (Study Calendar and Appendix C). Repeat complete exam as clinically indicated.
 
Patients should have weekly symptomatic ocular assessments until the symptoms resolve to Grade 1 or baseline or are deemed to be irreversible by the investigator.
 
Repeat complete exam as clinically indicated, at least every other cycle (from point at which toxicity first reported) at a minimum
 
	
 
Hold mirvetuximab soravtansine dosing.
 
Patients may be allowed to resume mirvetuximab soravtansine reduced by one dose level after AE has resolved to Grade 1 or better within 28 days.
 
			
Grade 4	
 
Complete eye exam as outlined in Study Calendar and Appendix C Repeat complete exam as clinically indicated.
 
Patients should have weekly symptomatic ocular assessments until the symptoms resolve to Grade 1 or baseline (Study Calendar and Appendix C) or are deemed to be irreversible by the investigator.
 
Repeat complete exam as clinically indicated, at least every other cycle (from point at which toxicity first reported) at a minimum
 
	Permanently discontinue mirvetuximab soravtansine dosing.			
* Appendix C includes CTCAE version 5.0 Grade definitions for select ocular disorders					

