#### 6.3 **Re-treatment Criteria**

For a patient to begin a new cycle or continue a cycle of therapy after a dose modification, the following criteria must be met.

- Pre-treatment criteria as described in Section 5.2.2 with the following exceptions
  - $\circ$  Treatment-emergent ocular disorders, which must have recovered to  $\leq$  Grade 1 or baseline
  - $\circ$  Treatment-emergent pneumonitis which must have recovered to  $\leq$  Grade 1

If the patient does not meet these criteria, dosing with the two agents in the combination regimen will be delayed and the patient should be re-evaluated within 48-72 hours. Dosing with both agents may resume if these criteria have been met. If the adverse event can be attributed to one of the agents in the combination regimen, that agent will be held or discontinued as per the Dose Modification Guidelines

described in Sections 6.1 and 6.2 respectively; however, treatment with the second agent may resume provided all the other criteria are met. However, if the next cycle is delayed due to treatment-related toxicity longer than 12 weeks then the patient should be removed from study treatment. In such cases, continuation of study treatment may be considered for those patients who have experienced clinical benefit if agreed upon between the Overall PI and the Investigator.

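### Study Calendar footnote d stops mirvetuximab for any reported eye symptom, while Section 6.1.1 and Table 3 continue dosing at Grade 1

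*Combined protocol and SAP*

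**What the plan says.** Footnote d of the Study Calendar attaches to the ophthalmic examinations, the Schirmer test and the ocular symptom assessment. The symptom assessment takes place before each cycle. If it is positive, the instruction is: "If the subject reports ocular symptoms then IMGN853 will be stopped and the subject will then be" sent to an ophthalmologist for a full examination. A parenthesis then refers to the full protocol for detail. No grade is mentioned.

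Section 6.1.1 treats referral and dosing as separate actions.

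- Referral: "If a patient develops ocular symptoms of any grade, the patient is required to have a complete examination by an ophthalmologist".
- Dosing: the interruption applies at or above "CTCAE Grade 2 ocular symptoms, treatment with mirvetuximab soravtansine will be interrupted".

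Table 3 then gives the action by grade. Grade 1 is "Continue mirvetuximab soravtansine dosing". Grades 2 and 3 are a hold, with conditions for resuming. Grade 4 is "Permanently discontinue mirvetuximab soravtansine dosing".

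Two other places agree with Section 6.1.1. Section 6.3 makes a new cycle conditional on recovery of "Treatment-emergent ocular disorders, which must have recovered to" Grade 1 or lower, or baseline. Table 5, the general rule for adverse events, leaves the dose unchanged at Grade 1 or below.

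On which text governs, Section 5.1 says "Appropriate dose modifications are described in Section 6" and Section 5.4.2 says "The management and dose modification for ocular symptoms is outlined in Section 6". The opening of Section 6 and the text of Section 6.1.1 likewise direct the reader to the tables that follow them.

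**The concern.** For a patient with mild eye symptoms, the calendar says to stop the drug and the dose-modification section says to give it. The calendar also requires assessments to be done before any study agent is given, so staff working from it meet footnote d at the moment they decide whether to dose.

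Two things are at stake.

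- **Consistency.** This is a multi-center trial, and sites could handle identical Grade 1 events differently. Appendix B (Section 3.9.1) requires every departure from the protocol's procedures to be reported to the sponsor and the IRB of record. Whichever instruction a site follows, it departs from the other.
- **Dose delivery.** Section 6 asks that treatment be kept to the planned dose and schedule wherever possible. Section 6.1.1 reports that plasma exposure was related to response as well as to ocular events. Holds that Section 6 does not call for work against that aim. The documents do not allow the effect to be sized.

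**Working it through.** No arithmetic is involved beyond two counts. The check is whether the instructions differ, at which grades, and whether any patient can meet both.

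**Step 1. Compare the initial action by grade.** The inputs are footnote d, Section 6.1.1 and Table 3.

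| Grade of symptomatic event | Footnote d | Section 6.1.1 and Table 3 | Agree on giving drug? |
|---|---|---|---|
| 1 | Stop | Continue | No |
| 2 | Stop | Hold | Yes |
| 3 | Stop | Hold | Yes |
| 4 | Stop | Discontinue permanently | Yes |

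They conflict at 1 of 4 grades.

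**Step 2. Check that Grade 1 can be a reported symptom.** Footnote d is triggered only by a symptom the patient reports, so a symptom-free Grade 1 finding creates no conflict. Appendix C grades four ocular terms:

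- Dry eye: Grade 1 includes mild symptoms that lubricants relieve. Can be symptomatic.
- Eye disorders, other: Grade 1 includes mild symptoms. Can be symptomatic.
- Blurred vision: Grade 1 is defined only by no intervention being indicated. Since blurred vision is itself a complaint, it is counted as symptomatic; this is an inference.
- Keratitis: Grade 1 is asymptomatic only. Does not trigger the footnote.

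That is 3 of 4 terms, or 2 of 4 if the inference about blurred vision is not accepted. Either way the overlap exists.

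**Step 3. Ask whether the situation is likely to arise.** Section 2.2 lists blurred vision, dry eye and keratopathy among the most common events with mirvetuximab monotherapy, and says most treatment-emergent events were Grade 2 or lower. It gives no Grade 1 ocular rate, so no count of affected patients can be derived.

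**Step 4. Decide which text is out of line.** Sections 5.1 and 5.4.2, the opening of Section 6 and Section 6.1.1 all place dose modification in Section 6 or its tables. Table 5 and Section 6.3 agree with Table 3. Footnote d stands alone. Its wording looks like a merger of the any-grade referral with the Grade 2 interruption.

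**The case against.** The best case for leaving the text alone has four parts.

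1. **The footnote defers to the protocol.** Its sentence ends by pointing to the full protocol. Footnote d already lists the components of the eye examination, so the pointer could be meant for the graded management in Section 6.1.1. But it directly follows the mention of the examination and puts no limit on the instruction to stop. If it does lead to Section 6.1.1, the reader arrives at text that says the opposite for Grade 1.

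2. **Stop may mean pause, examine, grade, then apply Table 3.** Appendix C separates the higher grades largely by corrected visual acuity, so the grade may not be known when a symptom is first reported, and Table 3 does not say what to do in that interval. This reading is workable when the grade is uncertain, and that part stands. It does not help when the symptom is plainly Grade 1 at the visit: Section 6 then requires no pause and the footnote still imposes one.

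3. **Section 6 governs anyway, and the texts are meant to be read together.** Section 6.1.1 and Table 3 point back to the Study Calendar, though for examinations rather than dosing. The pointers do show which text to correct. They are not an explicit precedence rule, and the footnote is mandatory and unqualified.

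4. **The consequence is small.** The error is toward caution, a brief pause could fit within the plus or minus 3-day dosing window, and no documented case or rate of divergent handling exists. All of this stands. It limits the importance of the point but does not remove the contradiction.

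**Conclusion.** The concern holds. Footnote d and Section 6.1.1 with Table 3 give opposite dosing instructions for symptomatic Grade 1 ocular events, and only for those. At Grades 2 to 4 all the texts withhold the drug initially.

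Following the footnote exposes no patient to more drug than Table 3 allows. The two-stage decision rules, the endpoints and the sample size are unaffected. The practical cost is unneeded holds and uneven handling across sites, of a size the documents do not allow to be estimated.

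The conclusion rests on reading Section 6 as the governing text, which the plan's own cross-references support, and on Appendix C allowing symptoms at Grade 1, which it states for dry eye and for other eye disorders. It should be fixed, because it is an operative dosing rule met before every cycle and not background text.

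**What to change.** Replace the stopping sentence in footnote d with wording such as:

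*For ocular symptoms of any grade, refer the participant to an ophthalmologist for a complete examination. Continue, hold or discontinue IMGN853 by grade, as set out in Section 6.1.1 and Table 3.*

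Notify the sites of the change.

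The cost is a one-sentence amendment and a site notice. No new data item is needed: adverse events are already graded by CTCAE (Section 7.2) and all are reported on the toxicity case report forms (Section 7.10). Analysis and sample size do not change.

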#### **MEASUREMENT OF EFFECT**

Measurement of effect will be assessed by both the Response Evaluation Criteria in Solid Tumors (RECIST) Version 1.1 and by the Immune-related Response Criteria Derived from RECIST 1.1 (irRECIST).

